- k. EOT, Day 42, Day 84 and Follow-up assessments are required for all participants. Participants with a successful overall response are required to return for all these visits. Participants withdrawn from study intervention or with an unsuccessful overall response prior to Day 42 are required to return to conduct a clinic visit for the EOT visit but will not be asked to return for the Day 42 or Day 84 visits; however, the participant will be contacted by telephone to obtain survival status at these time points. For participants with IM, survival status on Day 126, Day 168 and Day 180 should be collected. A Follow-up visit will be performed 4 weeks (± 7d) after last dose of isavuconazole administration.
- l. If clinically indicated.
- m. If EOT occurs within 1 week of a scheduled visit, the visits and assessment can be combined; however, the schedule of assessments for EOT must be applied.
- n. 12-lead ECG is performed 15 minutes prior to the end of the first daily infusion or approximately 3 hours post oral dose during the treatment period.
- o. If the assessments are performed at screening, the additional assessments between Day 1 and Day 7 are not required.
- p. Applicable for participants continuing on study intervention.
- q. For participants with IA or other filamentous fungi infection other than IM, if study treatment needs to be extended to longer than 84 days, sponsor should be notified. For participants with IM, procedures on Day 84, Day 126 and Day 168 should follow requirements of Day 42, maximum of study treatment is 180 days or until EOT visit.
- r. GM antigen will be tested at screening. If clinically indicated, it can be tested during Day 1 to Day 7 for participants with IA only. Any 1 of the following: 1) A single serum or plasma value ≥ 1.0 ; 2) BAL fluid ≥ 1.0 ; 3) single serum or plasma: ≥ 0.7 and BAL fluid ≥ 0.8 ; 4) two consecutive values of either serum, plasma or BAL fluid between ≥ 0.5 to <1.0 (from two separate specimens of the same category) is considered a positive result. GM meeting the protocol defined requirements within 7 days prior to first dose of study drug are eligible for enrollment.
- s. Radiology imaging obtained within 1 week (if available) prior to screening could be used.
- t. Samples/assessments obtained within 72 hours prior to screening could be used.

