Participants will be treated until they reach a defined discontinuation criterion (see [Section 7.1](#)), up to a maximum of 84 days (up to 180 days for participants with IM).

Participants who are considered by the investigator to have experienced a successful overall outcome will continue treatment for a minimum of **7 days** after resolution of all clinical symptoms and physical findings. The maximum treatment period of 84 days (180 days for participants with IM) must not be exceeded.

Non-study systemic antifungal medication is only allowed after the Day 42 visit, unless the participant has failed treatment with study medication prior to the Day 42 visit.

Participants with a successful overall response at EOT (prior to Day 42) must return for Day 42 and Day 84 visits, even if they are no longer under study treatment. It is recommended to keep participants on study treatment up to Day 42 if the administration of systemic antifungals as prophylaxis is anticipated after the end of study treatment.

Participants with an unsuccessful overall response at EOT and requiring alternative systemic antifungal therapy will not be asked to return for Day 42 and/or Day 84 visits; however the survival status at these time points will be collected. A Follow-up visit will be performed 4 weeks (± 7 d) after last dose of isavuconazole administration.

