8.2. Efficacy Assessments

All efforts should be made to have EOT assessments performed in all participants. Participants with a successful overall outcome at EOT (prior to Day 42) must return for Day 42, Day 84, or other planned visits (eg, Day 126 and Day 168 for participants with IM) through EOT as specified in [SoA](#), even if they are no longer receiving study intervention. If administration of systemic antifungals as prophylaxis is anticipated following successful therapy, participants should remain on study intervention through the Day 42 visit, ie, do not start any non-study systemic antifungal medication until after the Day 42 visit.

Secondary prophylaxis for participants who are expected to receive additional courses of chemotherapeutic agents, undergo BMT/HSCT, or are anticipated to remain significantly immunosuppressed is acceptable after the Day 42 visit. Reasons for requiring secondary prophylaxis must be documented in the eCRF.

Participants withdrawn from study intervention or with an unsuccessful overall outcome at EOT and requiring alternative systemic antifungal therapy will not be asked to return for subsequent visits, but will be required to return for the FU visit which is planned on 4 weeks after the last dose of study intervention; however, the survival status at the time points as specified in [SoA](#) will be collected (confirmation by phone contact is acceptable and will be documented in the eCRF).

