8.2.8. Investigator's Assessment of Overall Response

The investigator's assessment of overall response will be recorded at Day 42, EOT and Day 84. For participants who had an overall response of failure at EOT (prior to Day 42 visit), assessment of response is not required on Day 42 and Day 84.

The investigator will be asked to provide his/her opinion of the participant's response as follows:

Clinical Response (all non-radiological clinical symptoms and physical findings):

- Resolution of all attributable clinical symptoms and physical findings
(ie, resolution of all clinical symptoms and physical findings of IFD present at baseline and/or resolution of those that appeared at a subsequent visit)
- Resolution of some attributable clinical symptoms and physical findings
(ie, resolution of some but not all clinical symptoms and/or physical findings of IFD present at baseline and/or of those that appeared at a subsequent visit)

- No resolution of any attributable clinical symptoms and physical findings and/or worsening

(ie, no resolution or worsening of any clinical symptoms and/or physical findings of IFD present at baseline and/or of those that appeared at a subsequent visit)

- Results not available/participant unevaluable

(ie, visit and/or assessment of clinical symptoms and physical findings of IFD was not performed at any time point [Day 42, EOT or Day 84])

- No attributable signs and symptoms at screening

(ie, no clinical symptoms or physical findings of IFD present at baseline)

Radiological Response:

- $\geq 90\%$ improvement
- $\geq 50\%$ to $< 90\%$ improvement
- $\geq 25\%$ to $< 50\%$ improvement
- $< 25\%$ improvement
- No signs on radiological images at screening (Proven IFD only)
- Results not available (ie, visit and/or radiological assessment was not performed at any time point [Day 42, EOT or Day 84])

Radiological assessments should be made by CT and all radiological images and local reports pertaining to IFD will be based on investigators' discretion.

Mycological Response:

- Eradication
(eradication of the original causative organism cultured or identified by histology/cytology at baseline)
- Presumed eradication
(missing documentation of the eradication of the original causative organism at baseline plus resolution of all or some clinical symptoms and physical findings of IFD present at baseline and/or of those that appeared at a subsequent visit)

- Persistence

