9.1. Statistical Hypotheses

No formal statistical hypothesis testing will be conducted for efficacy analysis.

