6.2.3.1.1. Subgroup Analysis

If data permit, subgroup analyses will be performed for the overall response based on investigator's assessment at EOT based on mITT population for the aforementioned subgroups in Section 6.2.1.3, and the IFD location [lower respiratory tract disease (LRTD) only, LRTD plus Other Organ, Non LRTD only] .

6.2.3.2. The Crude Rates of Overall Response at Day 42 and Day 84

- Estimand strategy: While on-Treatment (Section 2.2.2).
- Analysis set: mITT and myITT-IA populations (Section 4).
- Analysis methodology: The crude rates of overall response based on investigator's assessment will be summarized by number and percentage of participants at Day 42 and Day 84, respectively. The 2-sided 95% CIs for crude rate will be calculated based on a binomial distribution.
- Intercurrent events and missing data: All data collected after use of the prohibited medications will be excluded. Missing data will be handled as described in Section 5.3. A participant that investigators' assessment indicated as Not Done at a visit will be considered as missing and will be included as a failure for the visit. Any death before Day 42 will be considered a failure by including in the death category for both timepoints. Any death occurring between Day 42 and Day 84 will be considered as a failure by including in the death category for Day 84.

6.2.4. Crude Success Rates of the Clinical, Mycological, Radiological Responses at EOT, Day 42 and Day 84

6.2.4.1. Clinical Response at EOT, Day 42 and Day 84

Outcome	Clinical response
Success	1. Resolution of all attributable clinical symptoms and physical findings 2. Resolution of some attributable clinical symptoms and physical findings
Failure	1. No resolution of any attributable clinical symptoms and physical findings and/or worsening 2. Results not available/Patient unevaluable
NA	No attributable signs and symptoms present at screening

- Estimand strategy: While on-Treatment (Section 2.2.2).

- Analysis set: mITT and myITT-IA populations (Section 4).
- Analysis methodology: Number and percent of participants in the categories of Success and Failure will be summarized at Day 42, Day 84 and EOT. The 2-sided 95% CIs for crude success rate will be calculated based on a binomial distribution.

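### Footnote k both requires and excuses the Day 42 and Day 84 visits for a responder who stops isavuconazole before Day 42, and an excused visit is scored as an overall-response failure

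*Protocol*

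**What the plan says.** Five places in the protocol decide who comes back after stopping isavuconazole.

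- **1.3, footnote k.** It opens by requiring the EOT, Day 42, Day 84 and Follow-up assessments of everyone, and adds: "Participants with a successful overall response are required to return for all these visits". The next sentence covers "Participants withdrawn from study intervention or with an unsuccessful overall response prior to Day 42". They attend the EOT visit but are not called back for Day 42 or Day 84; survival is obtained by telephone.
- **6.1.1.** "Participants with a successful overall response at EOT (prior to Day 42) must return for Day 42 and Day 84 visits", even when off treatment. The exemption is narrow: "Participants with an unsuccessful overall response at EOT and requiring alternative systemic antifungal therapy will not be asked to return for Day 42".
- **7.1.** An intolerable AE is a listed reason for stopping study intervention, and participants who stop are to remain in the study for evaluation.
- **8.2.** EOT successes before Day 42 must return even if off drug. The exemption then reads: "Participants withdrawn from study intervention or with an unsuccessful overall outcome at EOT and requiring alternative systemic antifungal therapy will not be asked to return".
- **8.2.8.** For participants who were overall failures at EOT before Day 42, "assessment of response is not required on Day 42 and Day 84". No other group is given this waiver.

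On scoring, Protocol 8.2.9 and 9.1.1.3 make a participant who is not available for assessment an overall-response failure. SAP 6.2.3.2 says that an assessment recorded as not done at Day 42 or Day 84 "will be considered as missing and will be included as a failure for the visit". The SAP has no separate rule for a visit that the protocol itself excused.

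**The concern.** In footnote k the word joining the two exempt groups is an or, so withdrawal from study intervention is enough by itself to excuse the visits, whatever the response. A participant who is responding but stops for tolerability is therefore told to return by one sentence and not to return by the next.

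This matters because the visit rule feeds a missing-equals-failure rule. Someone who attends can be a success at Day 42 and Day 84. The same person, followed by telephone, is a failure without having been examined. The classification then depends on which sentence the site applied and not on the course of the infection, and in the reported rate such a failure cannot be told apart from an observed one.

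**Working it through.** **The plan's own figure.** The only design probability is 86.6% in Protocol 9.5: 1 − 0.97^66 = 0.866, which reproduces. It concerns detection of adverse events and has no bearing here. The plan gives no figure for early stopping among responders, so the check is mainly a comparison of the texts.

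**Test case.** A participant has a successful overall response at EOT, stops at Day 20 for an intolerable AE, and starts no other systemic antifungal.

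| Text | Day 42 and Day 84 visits |
|---|---|
| 1.3 footnote k, sentence on successes | Return |
| 1.3 footnote k, sentence on withdrawal | Not asked to return |
| 6.1.1 | Return |
| 8.2, sentence on successes | Return |
| 8.2, sentence on withdrawal | Not asked to return, unless the antifungal condition also qualifies withdrawal |
| 8.2.8 | Assessment not waived, because the participant is not an EOT failure |

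**Scoring if the visits are excused.** SAP Appendix 3 sets the Day 42 window at days 2 to 49 for clinical and mycological response and days 8 to 49 for radiological response. The Day 84 window is days 50 to 91. Overall response is not listed in that table.

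| Endpoint | Day 42 | Day 84 |
|---|---|---|
| Overall | No window given; not done = failure | Failure |
| Clinical | Day 20 EOT assessment may fill it | Nothing in window; failure |
| Radiological | Day 20 EOT assessment may fill it | Nothing in window; failure |
| Mycological | Day 20 EOT assessment may fill it | Unclear: SAP 6.2.4.2 lists no follow-up result as NA, but not done as failure |

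At Day 42, component successes could thus stand beside an overall failure. Footnote m lets EOT be combined with a scheduled visit within one week, so a stop from about Day 35 (42 − 7) can serve as the Day 42 visit. No stop before Day 42 reaches the Day 84 window. The Follow-up visit, due around Day 48 in this example (20 + 28), is no substitute, because the schedule places no investigator response, radiology or mycology assessment there.

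**Size per participant.** Response is analysed in mITT and myITT-IA. One participant moved from success to failure lowers the crude rate by 1/n. The mITT size is not stated, so n = 30 to 50 is assumed:

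- n = 30: 1/30 = 3.3 points
- n = 50: 1/50 = 2.0 points
- if all 66 expected treated participants were in mITT: 1/66 = 1.5 points

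**Illustration, with assumed n = 45 and 22 responders (exact 95% CIs).**

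- None excused: 22/45 = 48.9% (33.7 to 64.2)
- One excused: 21/45 = 46.7% (31.7 to 62.1)
- Three excused: 19/45 = 42.2% (27.7 to 57.8), a shift of 3/45 = 6.7 points

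**The case against.** **Most of the text points one way.** Section 6.1.1, one sentence of 8.2 and one sentence of footnote k all tell EOT successes to return, 8.2.8 waives assessment only for failures, and the schedule describes itself as an overview. The 8.2 exemption can also be parsed so that the need for alternative antifungal therapy qualifies both groups, which brings it close to 6.1.1. All of this stands as evidence of intent. It does not remove the withdrawal clause of footnote k, which has no such qualifier and is in the schedule that other sections send the reader to.

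**Participants who were not successes at EOT.** A reader might infer that those who stop without having responded, or who fail between Day 42 and Day 84, are also misclassified, since the sections differ on their visits too. They are not: 8.2.9 carries an overall failure forward, so overall response is failure whether or not they attend.

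**Day 42 components.** It is tempting to say that every Day 42 response becomes an automatic failure. The windows in SAP Appendix 3 do not support that for clinical, mycological and radiological response.

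**Later antifungal therapy.** A responder who requires another systemic antifungal before the time point is a failure under 8.2.9 in any case. Only those who start none are affected.

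**The estimand.** Estimand 2.3 is labelled while on treatment, so off-drug visits might seem irrelevant. However, its stated rule excludes only data after prohibited medication, and the protocol requires off-drug responders to attend. Even a strict on-treatment reading would keep the status at stopping and would not impute failure.

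**Stakes.** Response is a descriptive secondary endpoint: "No formal statistical hypothesis testing will be conducted for efficacy analysis". That limits the consequence to the accuracy of a reported rate.

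**Conclusion.** The contradiction is real and sits in current text. It concerns one group: participants with a successful overall response at EOT who are withdrawn from isavuconazole before Day 42 and start no other systemic antifungal. If excused, they are scored as failures for overall, clinical and radiological response at Day 84, and for overall response at Day 42. EOT response is safe because the EOT visit is always required. Mortality is protected by the telephone check, and the primary safety endpoint is not involved.

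Each such participant moves the rate by 2.0 to 3.3 points, on the assumption of an mITT of 30 to 50. How many there will be cannot be derived from the documents, so no total shift can be claimed. A reader might conclude that the Day 42 and Day 84 rates no longer describe infection outcome, or that sites will in fact differ. The documents show only that the wording permits different handling. The point merits correction because the rates come from a small single-arm study and the error runs in one direction, against response.

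**What to change.** Reconcile footnote k and 8.2 with 6.1.1 and 8.2.8. State that a participant with a successful overall response at EOT who stops isavuconazole before Day 42, for whatever reason, returns for the scheduled Day 42 and Day 84 response assessments, and that withdrawal from study intervention alone is not a ground for telephone-only follow-up. Participants who are failures at EOT need no added visits, since their overall response is already settled.

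In the SAP, report failures due to a visit not done separately from assessed failures at Day 42 and Day 84.

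The cost is wording in two places of the protocol and one extra row in the response tables. A few participants who stopped early would attend visits already in the schedule, which is some burden for people who may have stopped for tolerability.

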1.3.1. Pharmacokinetic Sampling Schema

Visit Identifier															
Study Day	Day 3		Day 7 ^e						Day 14 ^e						EOT
Hours ^a	Predose (0)	1.5 ^d	Predose (0)	1.5 ^d	3	6	12	24	Predose (0)	1.5 ^d	3	6	12	24	Predose (0) or 24 ^b
PK blood sampling	X ^c	X ^d	X ^c	X ^d	X	X	X	X	X ^c	X ^d	X	X	X	X	X ^c

- Nominal time (hours) after start of infusion or capsule intake.
- For EOT, blood sample will be predose or exceptionally, 24 hours after last dose.
- Blood will be drawn within 1 hour prior to the administration of study intervention.
- Blood will be drawn anytime within 15 minutes prior to or 15 minutes after stopping study intervention administration if IV infusion or 1.5 ± 0.15 hours after study intervention dosing if oral administration. For IV infusion, if the PK sampling time window has overlap with next one due to infusion period, it is suggested to collect different PK sample according to their own time window, respectively, if possible.
- On Day 7 and Day 14, additional blood will be drawn at 3 hours, 6 hours, 12 hours, and 24 hours (24 hours PK sample should be collected prior to the administration on Day 8 and Day 15) after study intervention administration.

2. INTRODUCTION

Cresemba®, isavuconazonium sulfate, is the water-soluble prodrug of the active triazole isavuconazole, which is an antifungal agent for the treatment of adults with IA and IM through inhibition of lanosterol 14- α -demethylase, a microsomal P450 enzyme (P45014DM) essential for ergosterol biosynthesis in fungi. Cresemba was approved in China for the treatment of IA and IM in adults in January 2022 and December 2021, respectively.

2.1. Study Rationale

This single arm, prospective study is a commitment to regulatory authority, and is designed to further evaluate the safety profile and the effectiveness of isavuconazole in a relatively larger Chinese population who will receive isavuconazole treatment in a post-marketing setting. The isavuconazole dose and regimen to be administered in this study are completely in accordance with the approved prescribing information.

A total of 62 Chinese participants were included in 2 completed clinical studies, as part of the global development program for IA and IM. One was a China-alone Phase 1 study in 36 healthy volunteers (Study 9766-CL-0038) which was completed in 2012, and the other was the global Phase 3 pivotal study conducted in patients with IA (SECURE Study, 9766-CL-0104) in which a total of 26 Chinese participants were enrolled, which was completed in 2013.

In a China-alone Phase 1 study (9766-CL-0038) in 36 healthy Chinese volunteers, single and multiple doses of oral and IV 200 mg isavuconazole were safe and well tolerated by male and female Chinese participants. In this study, the mean plasma C_{max} and AUC values were generally higher compared with participants from Western countries (Table 1).

Table 1. Comparison of Isavuconazole Exposure in Healthy Chinese and Western Participants after Single- and Multiple-Dose Oral Administration of Isavuconazonium (200 mg eq. Isavuconazole)

Parameter	Single Dose		Multiple Dose	
	Chinese Subjects	Western Subjects	Chinese Subjects	Western Subjects
Study	9766 CL 0038	9766 CL 0041	9766 CL 0038	9766 CL 0017
n	12	24	12	37
C_{max} (μ g/mL)	3.391 (0.500)	2.318 (0.524)	8.891 (1.651)	7.499 (1.893)
AUC (μ g \times h/mL) [†]	116.4 (36.3)	96.26 (27.7)	140.4 (32.8)	121.4 (35.8)

Values of pharmacokinetics parameters are mean (SD).

[†]AUC = AUC_{inf} for single dose results, AUC_{tau} for multiple dose results.

Source: 9766 CL 0038 Tables 12.4.2.1.1, 12.4.2.3.1; 9766 CL 0017 Table 12.4.2.1; 9766 CL 0041 Table 12.4.2.1.

A 2-compartment population PK model was developed that included data from Phase 1 and Phase 3 studies. Chinese participants were found to have, on average, a 40% lower clearance compared with participants from Western countries. Monte Carlo simulations were then performed using mean population estimates. Based on the safety profile and PK/PD modeling and simulation for the antifungal activity of isavuconazole, the differences were not considered clinically significant. No dose adjustment is required for the Chinese population.

In the pivotal controlled study (SECURE Study, 9766-CL-0104), there were in total 26 Chinese participants who received at least 1 dose of study intervention, among them 10 participants were randomized to receive isavuconazole. Analysis of the efficacy in the China sub-group in SECURE Study showed the primary efficacy endpoints of all-cause mortality by Day 42 to be 10% (1/10) in the isavuconazole group and 25% (4/16) in the voriconazole group (difference of -15.0% with 95% CI [- 43.2%, 13.2%]). In general, efficacy of isavuconazole in Chinese participants was consistent with the findings in the overall population, indicating comparable mortality and overall response rates in the isavuconazole and voriconazole treatment groups. The safety profile was also comparable in Chinese participants to the overall population.

In summary, the clinical data of isavuconazole in Chinese population have been obtained from 46 Chinese participants including 36 healthy participants and 10 participants with IA. The overall PK, safety and efficacy of isavuconazole has been demonstrated in Chinese.

